Impacts of the Affordable Care Act

2) Objectives

The purpose of this study is to understand the impacts of the Affordable Care Act (ACA) in a safety net population. We will assess the following in states that expanded Medicaid compared to those that did not or among states that expanded Medicaid:

- Pre-post rates of health insurance status and payer mix
- Pre-post access to healthcare (i.e., visits, provider workforce, receipt of recommended healthcare services, receipt of chronic disease specific care and outcomes; receipt of preventive care, appropriate care for specialized populations such as cancer survivors and patients with multimorbidity/complex healthcare needs)
- Pre-post healthcare expenditures
- Pre-post changes in health disparities (e.g., low-income, racial and ethnic minorities, rural versus urban)

We will look at differences in access to healthcare, expenditures, and disparities among those who gained coverage in the post-period, those who already had coverage, those with intermittent coverage, and those who remained uninsured. We will also try to understand how aggregated measures of social determinants of health constructed from community-level geocoded data (i.e., fast food availability, parks, income distribution, and racial/ethnic breakdown) from publicly available sources, such as the US Census Bureau, change the impact of disparities, access, and receipt of healthcare in relation to gaining or not gaining health insurance.

We propose to investigate how complex, and early-onset diseases affect the receipt of healthcare services later in life. Some of these analyses will focus on sub-group populations including patients with a history of cancer and those with multiple or complex chronic conditions. To accomplish these analyses, we will examine data from patients of all ages as many childhood cancers have a high likelihood of survival, and it is important to identify these patients as they are likely to have additional healthcare needs throughout their lifespan.

3) Background

Health insurance facilitates access to care and reduces unmet healthcare needs,¹⁻⁴ yet 47 million Americans had no coverage in 2012.⁵ The ACA, the largest healthcare-related legislation in the United States (US) since Medicare's establishment in 1966, was enacted with the goal of expanding coverage to all citizens and legal residents.⁶ The ACA increases opportunities to gain health insurance, including expansions in Medicaid coverage to individuals earning \leq 138% of the federal poverty level (FPL) and the establishment of health insurance marketplaces. In 2012, the Supreme Court ruled that states were not legally required to implement Medicaid

expansions, and those opting out could not be penalized.⁷ As of December 2014, 27 states (and D.C.) implemented the expansion;⁸ the number of states is increasing. Many persons directly affected by these expansions are seen at community health centers (CHCs), which comprise much of our nation's healthcare 'safety net' and serve a rapidly increasing number of patients;⁹ in 2012, 36% of CHC patients were uninsured.¹⁰ The effect of the ACA on health insurance coverage and access to health care services is unknown, thus it is imperative to assess its impact.

4) Study Design

Secondary data analysis.

We will use electronic health record (EHR) data from the Accelerating Data Value Across a National Community Health Center Network (ADVANCE) clinical data research network (CDRN) data warehouse and Oregon Medicaid administrative data.

The ADVANCE CDRN is a unique 'community laboratory' for research with underrepresented populations that includes patients receiving care in safety net clinics. The ADVANCE CDRN data warehouse includes *integrated* longitudinal outpatient EHR data from several organizations, including OCHIN, Health Choice Network, Fenway Health, and Legacy Health.

Oregon Medicaid administrative data will be linked to OCHIN Oregon clinics in the ADVANCE CDRN to assess the receipt of healthcare services outside the ADVANCE network clinics and all healthcare expenditures.

Additionally, we will partner with the state cancer registries of one or more states to complete probabilistic linkage between our patient population and reported cancer cases. It is currently unknown how well personal cancer history and related data are documented in the outpatient EHR (i.e., data contained in the ADVANCE CDRN), thus our ability to identify and characterize cancer survivors may be incomplete. A linkage with one or more state cancer registries will supplement the CDRN data by comprehensively identifying cancer survivors in our cohort. This will allow us to test and validate our EHR-based algorithms, and to evaluate post-cancer care services provided by community health centers and the impact of insurance coverage for this population.

5) Study Population

a) Number of Subjects

Approximately 2.3 million total possible subjects. All analyses will contain a subset of these subjects.

b) Vulnerable Populations

Children ages 0-18 will be included for methods development and analyses related to childhood cancer and long-term care for cancer survivors. There is little literature about childhood cancers in vulnerable populations (e.g., economically marginalized, uninsured, or Medicaid insured) and associated disparities. Furthermore, adults with a history of childhood or adolescent cancer may require special follow-up care and screening

throughout their adult lives, thus we wish to have access to their EHR records from earlier ages where available.

c) Setting

This research will be conducted in collaboration with OCHIN. OCHIN requests the OHSU IRB serve as the IRB of record for this study.

d) Recruitment Methods and Consent Process

All patients with data in the ADVANCE CDRN may be included in this study. Subsets may include only OCHIN EHR data, only Oregon OCHIN EHR data, only persons with certain diseases or conditions (*e.g.*, cancer, diabetes, obesity), etc. For analysis of expenditures, Oregon OCHIN clinics from the ADVANCE CDRN will be linked to Oregon Medicaid administrative data using Medicaid identification number; subjects found in both datasets will be included. Similarly, for cancer registry linkage analyses only patients identified in both datasets will be included in analyses.

The ADVANCE data was collected under a waiver of authorization as the data warehouse poses very little risk to patients, and it was not practical to consent the number of patients included in the dataset.

6) Procedures

Secondary data analysis will be conducted.

7) Data and Specimens

a) Sharing of Results with Subjects

Results will not be directly shared with subjects.

b) Data and Specimen Banking

No specimens are being collected. Data is not being banked for future research.

8) Data Analysis

We will summarize baseline measures using descriptive statistics and data visualization methods (*e.g.*, histograms, scatter plots) to characterize baseline data across clinic and state groups. We will estimate the differences in access and receipt of recommended health care. We will also assess health care expenditures. Our primary methodological approach will utilize difference-in-differences (DID) methodology. The DID approach has been frequently used by health economists and health services researchers to account for potential secular effects and changing policies that would affect both expansion and non-expansion states over time, while adjusting for potential confounders.¹¹⁻¹⁶

We will implement state random effects in clinic-level analyses and both clinic and state random effects in patient-level analyses to control for correlation of observations nested in clusters (*e.g.*, individuals nested in clinics which are nested in states). We recognize that the assumption for random effects may not be met and we will also assess the robustness of our

assumptions by running models that treat clinics and states as fixed effects. We will formally test the validity of the random effects using the standard Hausman test,¹⁷ as well as assessing overall qualitative differences that may arise between the random and fixed effects models.

We will use GLMM models,¹⁸ which offer flexible regression modeling to accommodate different sources of correlations (serial, intra-clinic, and intra-state), categorical and continuous covariates, and fixed and time-dependent covariates. These methods offer a wide range of parametric distributions to model the dependent variables, including logistic regression (binary data), beta regression (percent data), Poisson regression (count data), and Gaussian regression (normally distributed data). The distribution of the outcomes of interest will be examined before selecting an analysis model; specific models will be refined through an iterative process.

Potential variables included in the analyses	Description
Age	Categories
Sex	Male/female, other
Race	White, American Indian/Alaskan Native, Asian, Black, Native Hawaiian/Pacific Islander, Other
Ethnicity	Hispanic/non-Hispanic
Household Income	Federal poverty level; overall income; % FPL
Language Preference	English, Spanish, other, etc.
Clinic Information	Rural/urban; panel size; panel demographics; provider characteristics
Medicaid Expansion Status	ACA Medicaid expansion state/non-expansion state; date of expansion
Visits	Frequency and type of visits
Healthcare Need	Special need because of a chronic condition
Insurance	Coverage status and type at visit; changes in status and type over time; % covered over time
Continuity of Care	% of visits at the same site and with same provider; Continuity of Care Index
Service Utilization	Number and types of all billed encounters overall and yearly; all services received; disease specific services received; preventive services received; amount of time services are delayed
Expenditures	Categories; overall
Health outcomes	Biomarkers such as HbA1c, blood pressure, body mass index, cholesterol measurements, etc
Diagnoses	Number and type of chronic and acute conditions
Community Vital Signs	Community markers of social determinants of health (e.g., fast food availability, parks, income distribution, racial/ethnic breakdown, healthy food availability, income distribution, homeownership)
Cancer registry elements	Date of diagnosis, primary type, stage, sequence, histology, behavior, grade, insurance at diagnosis, family history, treatment, vital status, date of death

9) Privacy, Confidentiality and Data Security

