Study Population	Oregon Medicaid patients aged 18-64 years with a Medicaid ID or Medicaid insurance recorded in the OCHIN EHR ≥1 billed health care visit (excluding dental) from 184 Oregon CHCs in the OCHIN network linked to state Medicaid records during the study time period (1/1/2013–12/31/2014). N=135,514.
Exclusion Criteria	Patients with no Medicaid record on EHR who also did not have a Medicaid ID.
Independent Variables	Insurance cohort: (1) continuously Medicaid (Medicaid recorded at all visits); (2) continuously not Medicaid (Medicaid not recorded at any visit (patients could have Medicare, private, VA/Military, worker’s compensation, or no coverage); (3) Gained Medicaid: Medicaid not recorded for all visits in 2013 and Medicaid recorded at all visits in 2014; and (4) Discontinuously Medicaid: Any combination of visit coverage that did not follow the definitions above.
Dependent Variables	The primary outcome was agreement between EHR and Medicaid data in assigning patients to one of the four cohorts.
Covariates	Patient demographics (sex, age, race, ethnicity, language, household income represented as % FPL, urban/rural, number of common chronic conditions, and number of encounters), visit and provider types, and clinic-specific (department type and customers of OCHIN's billing service) characteristics. We included the following common chronic conditions assessed

	from diagnostic codes in the EHR: hypertension, diabetes, coronary artery disease, lipid disorder, and asthma/chronic obstructive pulmonary disorder.
Analysis Plan	Visit-level: agreement, prevalence-adjusted bias-adjusted kappa (PABAK), sensitivity, specificity, positive predictive value (PPV), and negative predictive value (NPV). Patient-level: 4x4 cross-tabulation, of insurance cohorts; two-stage logistic regression.
Data Set Name	PPDA Projects → InsuranceValidation → Data → CLEAN → patients.csv, patient_pre.csv, patient_post.csv, patient_ch.csv, encs_pre.csv, encs_post.csv, agree_no_final.csv Code is included under: PPDA Projects → InsuranceValidation → Final Code
Code Location	Box at OHSU

In Low-Income Latino Patients, Post-Affordable Care Act Insurance Disparities May Be Reduced Even More than Broader National Estimates: Evidence from Oregon

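### As written, the both-datasets rule makes the cancer-registry validation one-sided: sensitivity can be estimated, but over-calling of cancer by the EHR algorithms cannot be detected

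*Combined protocol and SAP*

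**What the plan says.** Both statements are in the IRB protocol (Impacts of the Affordable Care Act) within the combined protocol and SAP.

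Section 4, Study Design, says that "we will partner with the state cancer registries of one or more states" in order to "complete probabilistic linkage between our patient population and reported cancer cases". The reason given is that the quality of cancer history in the outpatient EHR is unknown, "thus our ability to identify and characterize cancer survivors may be incomplete". Of the linkage it says: "This will allow us to test and validate our EHR-based algorithms". A second use is to evaluate post-cancer care and the effect of insurance coverage in this group.

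Section 5d, Recruitment Methods and Consent Process, first sets a both-datasets rule for the Medicaid expenditure analysis. It then extends that rule by analogy: "for cancer registry linkage analyses only patients identified in both datasets will be included in analyses".

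Section 8, Data Analysis, lists cancer registry elements among the potential variables. It gives no validation method, accuracy measure or registry-negative comparison group. The separate SAP does not mention the registry linkage.

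**The concern.** A validation study compares an algorithm with a reference standard in people who have the condition and in people who do not. Here the reference is a file of cases. For such a file, finding no match is the negative reference result, so a rule that keeps only matched patients removes every reference-negative person before the analysis starts.

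The rule suits the expenditure analysis it is borrowed from, because a patient who is absent from the Medicaid data has no Medicaid spending to analyse. It does not suit a validation.

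At stake is whether the study can tell an accurate algorithm from one that labels too many people as cancer survivors. Section 2 of the IRB protocol plans analyses of patients with a history of cancer, and the linkage may cover as little as one state. If survivors elsewhere are identified from the EHR alone, the false-positive rate helps decide who enters those analyses. The documents do not describe that step, so this consequence is an inference.

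**Working it through.** **Inputs.** From section 4: the purpose (validation), the reference standard (reported cancer cases) and the coverage (one or more states). From section 5d: the inclusion rule. Section 5a gives only "Approximately 2.3 million total possible subjects". No number of linked patients, cancer prevalence or algorithm accuracy is stated, so there is no figure of the plan's to reproduce.

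**Step 1: the full table.** Cross-classify each EHR patient by algorithm result and registry status.

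| | Registry-positive | Registry-negative |
|---|---|---|
| EHR algorithm positive | TP | FP |
| EHR algorithm negative | FN | TN |

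**Step 2: apply the 5d rule.** Only the registry-positive column remains, so FP = 0 and TN = 0.

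- PPV = TP/(TP + 0) = 100% if the algorithm flags at least one retained patient.
- Specificity = TN/(TN + FP) = 0/0, undefined.
- NPV = 0/(0 + FN) = 0% whenever FN > 0.
- Sensitivity = TP/(TP + FN), unchanged, if being identified means having a person record in both datasets.

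If being identified instead meant being flagged as a cancer patient in both, FN would also be 0 and sensitivity would be 100% by construction. The results for PPV and specificity are the same under either reading.

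**Step 3: illustration.** All rates here are assumed: prevalence 1-5%, sensitivity 60-95%, specificity 97-99.9%, in a hypothetical 100,000 patients.

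| Prevalence | Sensitivity | Specificity | PPV, all patients | PPV, both-datasets set |
|---|---|---|---|---|
| 1% | 60% | 97% | 600/(600 + 2,970) = 16.8% | 600/600 = 100% |
| 3% | 80% | 99% | 2,400/(2,400 + 970) = 71.2% | 2,400/2,400 = 100% |
| 5% | 95% | 99.9% | 4,750/(4,750 + 95) = 98.0% | 4,750/4,750 = 100% |

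In the middle row, NPV in all patients is 96,030/(96,030 + 600) = 99.4%. In the restricted set it is 0/600 = 0%. Sensitivity is 2,400/3,000 = 80% in both.

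**Step 4: what imperfect linkage does once unlinked patients are kept.** Let TP, FN, FP and TN now refer to true cancer status. Suppose a fraction m of true cancers has no registry match, independently of the EHR flag.

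- Apparent PPV = (1 - m) x TP/(TP + FP), which is too low by the factor 1 - m.
- Apparent specificity = (TN + m x FN)/(TN + FP + m x (TP + FN)), a weighted average of the true specificity and 1 - sensitivity. It is too low for any useful algorithm, but only slightly when cancer is uncommon.
- Sensitivity is unchanged, and NPV is slightly too high.

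**The case against.** The strongest reply is that the 5d sentence is not an analysis specification. It stands in a recruitment and consent section, works by analogy with the expenditure rule, and may describe only the linked survivor cohort. The same section says that all patients with ADVANCE data may be included. Inclusion rules were adapted elsewhere: the Oregon expenditure paper lists no requirement for a health-center record, although 5d states a both-datasets rule for expenditures too. This reading is plausible. But the sentence covers registry linkage analyses without exception, validation is one of their stated purposes, and nothing else in the documents exempts it.

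The second reply is that the plan's stated worry is incomplete capture, which sensitivity answers. That stands: the validation is one-sided, not worthless.

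Third, no PPV or specificity is promised for the cancer algorithms. That also stands. The study's own Medicaid-coverage validation does list sensitivity, specificity, PPV and NPV, and it keeps a group continuously without Medicaid. This shows what the team regards as a full validation, though it does not bind the cancer work.

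A reader might go further and infer three things that the documents do not support:

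- That the excluded patients are simply false positives. Linkage is probabilistic and limited to one or more states, so an EHR-positive, unmatched patient may be a missed link, or a cancer diagnosed outside the linked state or its coverage years. These are apparent false positives only.
- That an algorithm which over-calls cancer would pass. No acceptance rule is stated.
- That the survivor-care analyses would be contaminated. Within the linkage analyses the rule keeps only registry-matched patients, so the question arises only where the EHR flag is used alone.

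**Conclusion.** The concern holds conditionally. If the 5d rule is applied to the validation, as its wording requires, specificity is undefined and PPV is 100% by construction, so over-calling of cancer cannot be detected. This is algebra and rests on one premise from section 4: that the registry data are reported cancer cases. That sensitivity survives rests on a further premise, that being identified means having a person record in both datasets.

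The size of any error in PPV cannot be stated. The 16.8% to 98.0% range reflects the assumed inputs and does not measure this plan. It shows only that the restricted set returns the same value for very different algorithms.

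The registry linkage is secondary. It belongs to none of Aims 1-3, and those analyses are unaffected. The inclusion rule should still be amended, because it undercuts a stated purpose of the linkage and is cheap to change.

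**What to change.** Amend the 5d sentence so that the both-datasets restriction applies only to analyses of care among registry-confirmed survivors. For algorithm validation:

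- include all CDRN patients resident in the linked registry's state during its coverage period;
- treat unlinked patients as registry-negative;
- report sensitivity, specificity, PPV and NPV;
- add a sensitivity analysis for linkage error and for cancers diagnosed out of area or before registry coverage.

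The cost is a short protocol edit plus that sensitivity analysis. The linkage is already planned against the patient population, so link status will be known, and the unlinked patients' EHR records are already in the CDRN. The downside is the bias in step 4 of the working: some true cancers will be counted as registry-negative, so PPV and specificity will be somewhat understated. Limiting the denominator to the registry's area and period reduces this, and the sensitivity analysis shows how much remains.

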This Data Use Agreement ("Agreement") with respect to a Limited Data Set is entered into by and between OCHIN Inc. ("OCHIN") and Oregon Health & Science University (OHSU) on behalf of OHSU Department of Family Medicine ("Data Recipient").

RECITALS

OCHIN and Data Recipient desire to set forth the terms and conditions under which OCHIN will disclose to Data Recipient certain Protected Health Information in the form of a Limited Data Set, as defined below, for the research described in this Agreement.

In consideration of the mutual promises below, and OCHIN's disclosure of the Limited Data Set to Data Recipient under this Agreement, the parties agree as follows:

ARTICLE I DEFINITIONS

As used in this Agreement:

- 1.1 "HIPAA" means, collectively, the Health Insurance Portability and Accountability Act of 1996 and regulations thereunder, as amended from time to time.
- 1.2 "Limited Data Set" means the information described in Exhibit A constituting a "limited data set" as generally defined in the Privacy Rule at 45 C.F.R. §164.514(e). Under the Privacy Rule, a limited data set contains Protected Health Information, can include specific identifiers, and must exclude others. A limited data set must **exclude** the following direct identifiers of an individual and his or her relatives, employer(s), and household members: names; postal address information (except town or city, state and zip code which are permitted); telephone numbers; fax numbers; electronic mail addresses; Social Security numbers; medical record numbers; health plan beneficiary numbers; account numbers; certificate/license numbers; license plate numbers and other vehicle identifiers and serial numbers; device identifiers and serial numbers; URLs; Internet Protocol (IP) address numbers; biometric identifiers including finger and voice prints; and full-face photographic and any comparable images. In the event of any conflict between this definition and the definition of a limited data set in HIPAA, the HIPAA definition will govern.
- 1.3 "Privacy Rule" means the Standards for Privacy of Individually Identifiable Health Information (45 C.F.R., Parts 160 and 164, Subparts A and E).
- 1.4 The following terms shall have the meanings given to them in HIPAA: "Breach," "Unsecured PHI," "Covered Entity," "Individual," "Protected Health Information," "Minimum Necessary," and "Required by Law."

ARTICLE II

1

[name] | www.ochin.org

DISCLOSURE

- 2.1. OCHIN intends to disclose to Data Recipient the Limited Data Set for the purposes of the research study entitled “**Post Affordable Care Act: Evaluation of Community Health Centers (PACE)**” which study is more specifically described in Exhibit A (the “Study”).
- 2.2 The Data Recipient represents that to the extent the Data Recipient requests that OCHIN disclose Protected Health Information to the Data Recipient as described in Section 2.1 and Exhibit A, such a request is only for the Minimum Necessary Protected Health Information for the accomplishment of the Data Recipient's purpose.
- 2.3 The Data Recipient shall provide OCHIN with the results of its Study as soon as practical.

**ARTICLE III
DATA RECIPIENT'S OBLIGATIONS**

- 3.1. Unless specifically stated otherwise in this Agreement, Data Recipient's obligations with respect to the Limited Data Set apply to the whole and to any part of the Limited Data Set, including any Protected Health Information contained in the Limited Data Set.
- 3.2. Data Recipient shall not use or disclose the Limited Data Set for any purpose other than the Study or as Required by Law. In addition, Data Recipient shall not use or disclose the Limited Data Set in any manner that would violate the Privacy Rule or any other HIPAA provision if done by a Covered Entity.
- 3.3. Data Recipient shall not disclose the Limited Data Set to any employee, other individual, or entity other than those employees, agents, or subcontractors specified in Exhibit A who are permitted to use or receive the Limited Data Set for the purposes of the Study (“Data Sub Recipients”).
- 3.4. Except as specified in Exhibit A, Data Recipient may not subcontract its performance obligations, or assign its rights, under this Agreement without the express written consent of OCHIN. Data Recipient shall ensure that any Data Sub Recipients, other than Data Recipient's employees, to whom it provides the Limited Data Set agree in writing to the same terms and conditions regarding the Limited Data Set that apply to Data Recipient under this Agreement.
- 3.5. Data Recipient must use appropriate safeguards to prevent the use or disclosure of the Limited Data Set in any manner not permitted by this Agreement.
- 3.6. Data Recipient must not identify or contact (or attempt to do so), either directly or through another person, any Individual in the Limited Data Set.
- 3.7. Data Recipient shall ensure that any agents to whom it provides the Limited Data Set agree to the same restrictions and conditions that apply to the Data Recipient with respect to such information.
- 3.8. Data Recipient agrees to mitigate, to the extent feasible, any harmful effect that is known

or becomes known to Data Recipient that arises from a use or disclosure of the Limited Data Set by Data Recipient or its employees or agents in violation of this Agreement or HIPAA.

- 3.9. Data Recipient must notify OCHIN within twenty-four (24) hours by phone, and in writing within five (5) business days, after Data Recipient becomes aware of any use or disclosure not authorized by this Agreement and any actual or suspected breach of Data Recipient's security. Data Recipient shall notify OCHIN within 5 days following the discovery of a suspected or actual Breach of Unsecured PHI. The Breach notice shall include the identification of each individual whose Unsecured PHI has been, or is reasonably believed by the Data Recipient to have been, accessed, acquired, or disclosed during the Breach, and any other information available that OCHIN will need to notify the affected individual(s). Data Recipient shall be responsible for payment of costs and will indemnify OCHIN for any reasonable expenses OCHIN incurs in complying with the Breach notification requirements where the Data Recipient or the Data Recipient's subcontractors or agents cause the Breach.
- 3.10. Data Recipient acknowledges that Data Recipient has no ownership rights in the Limited Data Set.
- 3.11. Within ten (10) business days of a written request by OCHIN, Data Recipient shall allow OCHIN to conduct a reasonable inspection of Data Recipient's facilities, systems, books, records, agreements, and policies and procedures relating to the use or disclosure of the Limited Data Set for the purpose of determining Data Recipient's compliance with this Agreement. Any failure of OCHIN to inspect or to detect or notify Data Recipient of an unsatisfactory practice does not constitute acceptance of the practice by OCHIN or a waiver of any remedy or right OCHIN has under this Agreement or applicable law.
- 3.12. Data Recipient shall comply with state laws to the extent that they are more protective than HIPAA of the Individual's privacy and security of the information contained in the Limited Data Set.

ARTICLE IV AMENDMENT AND TERMINATION

- 4.1 When OCHIN reasonably concludes that an amendment to this Agreement is necessary to comply with applicable law, OCHIN shall notify Data Recipient in writing of the proposed modification(s) ("Legally-Required Modifications"). Data Recipient shall be deemed to have accepted the Legally Required Modifications on the 30th day after it receives such notice unless, within that time period, Data Recipient delivers a written rejection of them to OCHIN. Data Recipient's rejection of a Legally Required Modification is grounds for termination of this Agreement by OCHIN on thirty (30) days written notice.
- 4.2. The following violations shall constitute cause for immediate termination by OCHIN of this Agreement:

3

4.2.1. A violation by Data Recipient of HIPAA as well as any other state or federal laws and regulations related to the use or disclosure of Protected Health Information or any information contained in the Limited Data Set;

4.2.2. Any breach of privacy or security by Data Recipient that is not properly disclosed to OCHIN pursuant to Section 3.8 and cured to the satisfaction of OCHIN;

4.2.3 Any use of data that is inconsistent with the authorized purposes described in this Agreement; and

4.2.4 Any violation of any provision of this Agreement, as determined by OCHIN.

At its sole discretion, OCHIN may give Data Recipient thirty (30) days to cure any such violations or breaches described in this Section 4.2.

4.3. On termination of this Agreement for any reason, Data Recipient shall return or destroy the Limited Data Set unless return or destruction is not feasible and Data Recipient explains why, in writing, to the address provided in this Agreement.

4.3.1. If Required by Law, Data Recipient may retain the portions of the Limited Data Set for the time specified as necessary to comply with the law.

4.3.2. Data Recipient's obligations under this Agreement shall continue until Data Recipient destroys the Limited Data Set or returns the Limited Data Set to OCHIN; provided however, that on termination of this Agreement, Data Recipient shall not further use or disclose the Limited Data Set except as Required by Law.

4.3.3. If Data Recipient elects to destroy the Limited Data Set, Data Recipient shall certify in writing to OCHIN that the Limited Data Set has been destroyed.

